10.2 Duration of Protocol Treatment

*(see Section 8.0 for response definition)*

- For complete responders, therapy will continue until progression (refer to Section 8.2)
- For partial responders, therapy will continue until progression.
- For stable patients, therapy will continue until progression (refer to Section 7.2).
- Patients who progress (treatment failure) will go off study at the time unequivocal progression is documented clinically and/or radiographically.

10.3 Therapy After Protocol Treatment is Stopped

At the discretion of the investigator.

10.4 Follow-up Off Protocol Treatment

All patients will be seen at 4 weeks after completion of protocol therapy. Continued follow-up required for all patients every 3 months to collect information on ongoing toxicities, late toxicities (including second malignancies) and survival data. This follow-up will continue until death or conclusion of the trial.

PROTOCOL DATE: 2018-MAY-30

CRI-CCTG: 0001

CCTG: IND.235

For patients who go off protocol treatment with CR/ICR, PR/iPR, SD/iSD or iUPD ongoing, tumor assessments will be required every 3 months until relapse (see Section 5.0 for investigations to be performed). Please note for patients who go off protocol treatment with iUPD, confirmatory scans should be performed at least 4 weeks, but no longer 8 weeks, after iUPD was documented.

A Death report will be required on all patients. Due within 2 weeks of knowledge of death (see Appendix IV- Documentation for Study).

## 11.0 CENTRAL REVIEW PROCEDURES

11.1 Central Radiology Review

As part of the trial, copies of x-rays and/or scans may be collected to evaluate cancer response to treatment. There will be no central radiology review for this study.

11.2 Central Pathology Review

There will be no central pathology review for this study.

## 12.0 CORRELATIVE STUDIES

A detailed Correlative Studies Manual will be provided on the CRI-CCTG-0001 trial specific website, which will include details regarding sample preparation, handling and shipping.

Specimens collected may be used by researchers now or in the future to better understand the nature of cancer and how patients respond to treatment. Samples will be used for research purposes only and will not be sold. Patients will not be identified by name. The only identification of tissue will be by a patient study number assigned at the time of randomization to the trial the surgical/histology number and/or patient initials. Material issued to researchers will be anonymized and only identified by a coded number.

Testing for hereditary genetic defects predisposing to malignant disease will not be carried out without the expressed consent of the patient).

All patients on whom a diagnostic tumor block is collected will be aware of this retrieval and will have given their consent.

### Genetic Testing

In the course of genetic testing for this study, there is a chance that “clinically relevant incidental findings” may occur; these refer to unanticipated discoveries made in the course of research but that are outside of the scope of the research [*TCPS2 2014*] being conducted. These findings could be inherited changes that might predispose a person to particular cancers or other diseases, and may be passed on in families.

The plasma cfDNA testing performed at screening and on-study will be done in a Clinical Laboratory Improvement Amendments (CLIA) laboratory. The panel is designed to identify somatic mutations and is not intended to detect the presence or absence of germline mutations. While common germline variants have been removed, the test may detect rare germline mutations.

During the informed consent process, participants will be told about the remote possibility of clinically relevant incidental findings being discovered, and given the opportunity to make informed choices about whether they wish to receive this information.

If a clinically relevant incidental finding is discovered during the testing for this study and a participant consented to learning about the results. These results will be included in the report provided directly to the study QI/AI. The QI/AI at the enrolling institution will be responsible for following local SOPs with regard to confirming the result, ensuring of genetic counseling is available, obtaining REB approval (if required) and contacting the study participant.

Germline testing may be performed on normal tissue as part of secondary and exploratory analyses. These analyses will be performed at study completion in the context of research in a non-CLIA certified laboratory. Therefore, these results will not be disclosed to the patient.

## 12.1 Protocol-Mandated Correlative Studies

### 12.1.1 *POLE and POLD1 Screening –Tumor Tissue and Blood Specimen (Mandatory for All Patients)*

Patients must have solid tumors that demonstrate POLE or POLD1 mutations identified at study entry via plasma cfDNA testing (PGDx) or tissue testing for POLE and POLD1 mutations (any CLIA-certified tissue assay).

- Patients enrolled onto the study via CLIA-certified tissue assay must also submit plasma for cfDNA testing (PGDx).
- Patients enrolled onto the study via plasma cfDNA testing (PGDx) must have tissue samples available (archival or fresh) for analysis, either a tumor block or two cores and a minimum of 20 slides of 4 micron thickness- less can be accepted if discussed with CCTG. Patients must be willing to consent to provision of archival tissue or fresh biopsy (optional).

Pre-treatment tumor tissue specimens that have been previously tested for POLE and POLD1 mutation testing using comprehensive genomic profiling will be allowed for trial entry and randomization. All patients must sign the pre-screening consent prior blood samples being sent.

A mandatory central testing for plasma cfDNA will be required for the primary endpoint. As such, two 10 ml tubes of peripheral whole blood will be collected from patients prior to randomization and sent for circulating tumor DNA (cfDNA) testing for identification of POLE and POLD1 mutations (PGDx). All patients will have POLE and POLD1 mutation testing centrally – patients randomized on the basis of archival tumor testing will have cfDNA testing of peripheral whole blood performed retrospectively.

Patients who do not have POLE/POLD1 mutations will not be eligible.

Diagnostic pathology reports are received as part of the supporting documentation required for this trial. A copy must be submitted at the time of Baseline Folder completion.

*Please refer to the CRI-CCTG-0001 Correlative Studies and Screening Manuals for details.*

### 12.1.2 *Tumor Tissue Collection*

The submission of a representative block of the diagnostic tumor tissue is mandatory for participation in this trial. Requests for this tissue will not be issued as these samples are expected to be submitted upon randomization for all patients. One tumor block and one adjacent normal tissue block are requested from any of the biopsies or resections of the tumor or solitary lesions following an initial response or biopsy samples collected upon progression. If no primary cancer blocks are available, one block of metastatic tissue can be sent instead.

Blocks are the preferred material to collect, as it is well known that tissue materials (including protein and nucleic acid integrity) on unstained sections deteriorate rapidly within 3-6 months after preparation. This will optimize the amount of tissue available to investigators and permit the preservation of the block submitted. If, at any time, the submitting hospital requires the block to be returned for medical or legal concerns, it will be returned by courier on request.

Where local center regulations prohibit submission of blocks of tumor tissue, the approval of the CCTG must be sought prior to randomization of the first patient to allow cores (two 2 mm cores of tumor from the block) or a minimum of 20 slides cut at 4 microns obtained from core biopsy, punch biopsy, excisional biopsy or surgical specimen to be substituted in response to the Central Tumor Bank request. If 20 slides are not possible, please contact CCTG to discuss.

Diagnostic pathology and genomic testing reports are received as part of the supporting documentation required for this trial. Receipt of these will initiate a request directly from the Queen's Department of Pathology to pathology departments for a representative tumor block.

Planned priority assays on tumor tissue include but are not limited to:

- POLE and POLD1 mutations,
- Whole-exome sequencing,
- RNA sequencing.

Where archival tissue is not available, patients will not be excluded if prior tumor testing identified POLE or POLD1 mutation and additional blocks/slides are not available.

#### 12.1.3 Blood Collection

The CCTG is interested in exploring the use of surrogate tissues such as blood, serum and plasma in evaluating potential prognostic or predictive biomarkers, or as evidence of pharmacodynamics effects. Some of the research blood collected will be tested for the following:

- T-cell subsets,
- Peripheral Blood Mononuclear Cells (PBMCs),
- HLA typing.

Detailed instructions for timepoints, sample acquisition, preparation, and shipping are found in the *CRI-CCTG-0001 Correlative Studies Manual*.

#### 12.2 Optional Fresh Tumor Biopsy

##### Banking of Tumor Tissue

Mandatory submission of tumor tissue has been described above. The subsequent banking of collected diagnostic tissue is not mandatory for participation in the study, but the participation of all centers is strongly encouraged. Blocks will be carefully banked as part of the CCTG tissue/tumor bank at Queen's University in Kingston, Ontario.

Patients will be required to sign an optional tissue consent. All patients who consent to the fresh tumor biopsy will have the biopsy performed at progression at the discretion of the treating investigator if feasible. Patients who consent to this procedure but a fresh biopsy is not possible will not be excluded from the study.

*Planned priority assays on tumor tissue include but are not limited to:*

- POLE and POLD1 mutations
- Whole-exome sequencing
- RNA sequencing

Proposals to use the banked specimens for the purposes of assessing markers involved in predicting treatment response and outcomes may be submitted to the bank. A scientific review process of any proposals to use the tissue will take place and any proposals approved will have undergone ethics approval.

### 12.3 Statistical Analyses

A variety of factors that could potentially predict clinical response to nivolumab and/or nivolumab in combination with ipilimumab will be investigated in peripheral blood (serum, plasma, and peripheral blood mononuclear cells (PBMCs)) and in tumor specimens taken from all patients prior to treatment, on study, and at progression and as outlined in Section 5.0. Data from these investigations will be evaluated for associations with response, survival (overall survival, progression free survival) and/or safety (adverse event) data. In addition, analyses of markers between the treatment arms will provide the necessary data to identify and validate biomarkers with predictive vs prognostic value. All samples collected may also be used for future exploratory analyses (unless restricted by local requirements) to assess biomarkers associated with immunotherapy treatment.

## 13.0 STATISTICAL CONSIDERATIONS

### 13.1 Objectives and Design

The primary objective for this randomized phase II open label and non-comparative trial is to evaluate efficacy as measured by objective response rate (ORR) by RECIST 1.1 of nivolumab monotherapy and of nivolumab combined with ipilimumab in randomized patients with advanced solid tumors with detectable POLE and POLD1 mutations as determined by plasma cfDNA. Secondary objectives include evaluating efficacy by ORR of nivolumab ± ipilimumab, duration of response (DOR), safety and toxicity in patients receiving nivolumab ± ipilimumab, and assess correlation between POLE/POLD1 mutations in tumor and POLE/POLD1 mutations in blood. Patients will be stratified by ECOG status (0 or 1) and number of prior treatments (0, 1-2, and  $\geq 3$ ), and randomized in 1:1 ratio to receive nivolumab alone or in combination with ipilimumab. The study will accrue up to 50 eligible and evaluable patients per treatment arm (100 total).

### 13.2 Endpoints and Analysis

The primary endpoint is ORR by RECIST 1.1 in immunotherapy naïve patients with advanced solid tumors with detectable mutations as determined by central blood-based assay (cfDNA for POLE/D1 mutations). Patients with detectable mutations in tissue but with no detectable mutations based on plasma cfDNA will be excluded from this analysis.

Response rates will be reported using percentages over all randomized patients with 90% exact confidence intervals (CI) of each arm in a non-comparative analysis. In addition, exact logistic regression models will be used to assess the effect of treatment on objective response probability, adjusting for mutational load values and trial site.

Secondary endpoints include: ORR of nivolumab monotherapy and of nivolumab combined with ipilimumab in all treated patients. Response rates will be reported using percentages over all patients who have received at least one dose of treatment with 90% exact CI of each arm in a non-comparative analysis. In addition, exact logistic regression models will be used to assess the effect of treatment on objective response probability, adjusting for mutational load values and trial site.

Duration of response (DOR) will be calculated from time of response to documentation of progression or death or censored at last time of disease assessment among all patients who have responded. Kaplan-Meier method will be used to estimate median duration of response and 90% confidence interval in each arm.

The responses assessed by iRECIST will be analyzed similarly as that by RECIST 1.1.

To assess the safety and characterize toxicities of nivolumab combined with ipilimumab and nivolumab monotherapy in all patients, estimation of the adverse event profile associated with treatment will be performed. All toxicities regardless of attribution will be reported using the CTCAE version 5.0 criteria. Adverse events rates will be reported using percentages with 90% exact CI.

Correlation between detectable mutations in tumor and detectable mutations in blood will be assessed by Fischer's exact test in each arm.

Detectable mutations in the initial study population are *POLE*/*POLD1* mutations based on plasma cfDNA.

PFS and OS of nivolumab monotherapy and of nivolumab combined with ipilimumab in patients with advanced solid tumors with detectable mutations as determined by plasma cfDNA, and in all treated patients (detectable mutations in tissue or cfDNA) will be evaluated as exploratory endpoints.

Kaplan-Meier method will be used to estimate probabilities of OS and PFS for each arm. Patients alive at the time of trial analysis will be censored as of the date of their last disease assessment. Medians and 90% CI will be provided, if available. No formal comparisons will be made between the two arms. Adjusted analyses will be also consider mutational load as one of the covariates.

Tumors will undergo whole exome and RNA sequencing to evaluate the genetic landscape of mutated tumors in responders versus non-responders to immune checkpoint blockade.

Detectable mutations in the initial study population are *POLE*/*POLD1* mutations based on plasma cfDNA.

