## Stratification

- ECOG performance status (0, 1)
- Number of prior treatments (0, 1-2, 3 or more)

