**Fig 1A. *POLE* mutation frequency across tumor types**

**Fig 1B. *POLD1* mutation frequency across tumor types**

## 2.3

### Immune Checkpoint Blockade in Tumors with High Mutational Burden

Cancer immunotherapy rests on the premise that tumors can be recognized as foreign rather than as self and can be effectively attacked by an activated immune system. An effective immune response in this setting is thought to rely on immune surveillance of antigens expressed on cancer cells that ultimately results in an adaptive immune response and cancer cell death [Schumacher 2015; Chen 2017]. These cancer-specific peptides resulting from neoantigens can be targets for T-cell recognition and effector responses. Tumors harboring defects in DNA repair proteins develop strikingly high rates of base substitutions during DNA replication with a subsequent mutation burden that is 10-20 fold higher than in tumors without these insults [Rayner 2016]. In NSCLC and melanoma, it has previously been shown that tumor mutational burden associates with sensitivity to checkpoint blockade with PD-1 blockade [Rizvi 2015; Snyder 2014]. In a cohort of 34 NSCLC patients, we found tumors with durable clinical benefit to anti-PD-1 therapy demonstrated high levels of nonsynonymous mutations and four cases (12%) harbored deleterious POLE and POLD1 exonuclease domain mutations. Pan-cancer genomic profiling of tumors also reveals a clear association between a hypermutated phenotype and mutations affecting DNA damage repair proteins (MMR deficient tumors and POLE mutated tumors seen in Figure 2 [Chalmers 2017; Zehir 2017]. These highly mutated tumors provoke a brisk immune infiltrate that is impaired through upregulation of inhibitory T-cell signaling via the programmed death -1 (PD-1) receptor pathway in the tumor microenvironment and cytotoxic T-lymphocyte Antigen 4 (CTLA-4) pathway in lymph nodes [Domingo 2016]. Given high levels of somatic mutations and increased tumor infiltrating lymphocytes (TILs), POLE and POLD1 mutated tumors present an attractive target for immune checkpoint blockade and case reports of POLE-mutated endometrial cancer and colorectal cancer (CRC) have shown a response to pembrolizumab [Castellucci 2017; Mehnert 2016].

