#### Randomization

Following receipt of the screening results, eligible patients will be randomized to one of two study arms.

The following additional information will be required:

- informed consent version date, date signed by patient, name of person conducting consent discussion and date signed
- tissue banking/optional consent version date
- confirmation of the requirements listed in Section 4.0, including dates of essential tests and actual laboratory values
- height and weight
- stratification factors

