6.2 Stratification

Subjects will be stratified at the time of randomization by:

- ECOG performance status (0, 1)
- Number of prior treatments (0, 1-2, 3 or more)

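### The exact logistic models for response adjust for mutational load and site but leave out both randomization stratification factors, with no reason given

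*Combined protocol and SAP*

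**What the plan says.** The Treatment Schema names two stratification factors: ECOG performance status (0, 1) and "Number of prior treatments (0, 1-2, 3 or more"). Section 6.2 repeats both under "Subjects will be stratified at the time of randomization by", and Section 13.1 confirms them: "Patients will be stratified by ECOG status (0 or 1) and number of prior treatments". Under Randomization in Section 6.1, the "stratification factors" are among the items a site must supply, so both are on file for every randomized patient.

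Section 13.2 reports response as percentages with "90% exact confidence intervals (CI) of each arm in a non-comparative analysis". It then adds an exact logistic regression to "assess the effect of treatment on objective response probability, adjusting for mutational load values and trial site". The same sentence and the same two covariates appear again for the secondary response rate in all treated patients. Response by iRECIST is to be handled in a similar way, so the covariate set carries over to it.

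For PFS and OS the plan says: "Adjusted analyses will be also consider mutational load as one of the covariates". It names no other covariate. Section 13 mentions the stratification factors only in the design paragraph and assigns them to no analysis.

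**The concern.** The sponsor thought ECOG status and prior treatment important enough to balance by design, yet the models of the treatment effect ignore them and adjust instead for site, which is not a stratification factor. An analysis that ignores the stratification makes no use of the balance it bought. If the factors predict response, two things follow:

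- The model without them estimates an odds ratio closer to 1 than the model with them. This is non-collapsibility: the two odds ratios are different quantities, and neither is biased.
- The test is more conservative than its nominal level, because the stratified design reduces chance imbalance and the analysis takes no account of it.

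The stake is the precision and interpretation of a supplementary analysis. In an open-label trial there is also a reason to settle the covariates in advance, so that their choice is not left open once responses are known.

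**Working it through.** **1. The plan's own figure, and whether it depends on these models.** Section 13.3 gives 50 evaluable patients per arm and 90% power for 13% v 30% (nivolumab) and 30% v 50% (combination), two-sided 0.10. These are one-sample tests:

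n = [(z₀.₉₅√(p₀(1−p₀)) + z₀.₉₀√(p₁(1−p₁))) / (p₁−p₀)]²

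- Combination: [(1.645×0.458 + 1.282×0.5)/0.20]² = 48.6, so 49. Normal-approximation power at 50 is 90.7%. The exact test (21 or more responses, upper tail 0.048) has 89.9%.
- Nivolumab: [(1.645×0.336 + 1.282×0.458)/0.17]² = 45.0, rounded up to 46, with power 92.2% at 50. The smallest exact n is 49 (11 or more responses). At exactly 50 the exact test needs 12 responses and has 86.1%, because of discreteness.

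The 50 per arm therefore reproduces within the usual variants. No covariate enters it, so the omission leaves it unchanged.

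**2. Scale for the between-arm models.** Section 13.2 gives no alpha or target difference for them. As a scale of precision only, take n=100, 30% v 50%, two-sided 0.10. The normal approximation gives about 66% power unadjusted; 90% would need 101 per arm.

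**3. Assumptions, none of them from the documents.** Half the patients are ECOG 1. Prior treatments 0 / 1-2 / 3+ are 10/50/40%. Permuted blocks of 4 are used within strata. Load is high/low 50:50 with log odds ratio 0 or 1.0. Intercepts are set so that the marginal response rates are 30% and 50%.

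| Scenario | ECOG log-OR | Prior-treatment log-ORs |
|---|---|---|
| inert | 0 | 0, 0, 0 |
| weak | −0.5 | 0, −0.3, −0.6 |
| moderate | −0.8 | 0, −0.5, −1.0 |
| strong | −1.2 | 0, −0.7, −1.5 |

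**4. Shift in the log odds ratio (calculated).** Solve for the intercept that gives 30% in one arm and 50% in the other, averaging over the factor distribution. The difference of the two intercepts is the log odds ratio with the factors in the model. Without factors or load it is ln(0.5/0.5) − ln(0.3/0.7) = 0.847.

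| | weak | moderate | strong |
|---|---|---|---|
| No load: omitted v included | 0.847 v 0.867 | 0.847 v 0.899 | 0.847 v 0.962 |
| Smaller by | 2.3% | 5.7% | 11.9% |
| Load in both: omitted v included | 0.896 v 0.916 | 0.892 v 0.944 | 0.887 v 1.002 |
| Smaller by | 2.2% | 5.5% | 11.5% |

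In the strong case with load, that is an odds ratio of exp(0.887) = 2.43 rather than exp(1.002) = 2.72.

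**5. Power of the exact test (simulated; p is twice the smaller exact tail).**

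| Power %, factors omitted v included | inert | weak | moderate | strong |
|---|---|---|---|---|
| (a) No load or site; included = six strata | 57.8 v 58.6 | 57.9 v 58.9 | 57.9 v 60.5 | 57.5 v 61.9 |
| (b) Load in both; included = main effects | 61.0 v 60.9 | 60.0 v 60.6 | 59.1 v 60.6 | 59.1 v 62.8 |
| (c) Load and eight uneven sites in both; change in points | +1.3 | not run | +2.7 | +4.0 |

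Row (a) uses 8,000 trials (paired SE 0.2-0.3 points) and row (b) 3,000 per scenario (paired SE 0.3-0.4). Row (c) uses only 150 per scenario, with prior treatments merged to two levels; the SE in the inert case is 0.9. Type I error against a nominal 10% in (b) is 6.9 v 6.9% (inert) and 5.5 v 6.5% (strong). In (c) it stays at or below 7.3%, and no conditional distribution was degenerate.

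**6. Sensitivity to stronger effects.** A large-sample logistic model without load or site, with ECOG log-OR 1.6 and 1.1 per prior-treatment level in absolute size, gives power 48% v 56%, type I error 6.8% v 10.4% and median log odds ratio 0.67 v 0.89. The 0 to 4 points are therefore not a ceiling.

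**The case against.** The strongest case against is that this is close to preference. The trial is non-comparative, the reported result is the per-arm rate with its interval, and the models come as an addition with no hypothesis or decision rule. The planned test keeps its level (5.5 to 6.9% against 10%), so it is valid without the factors. All of that stands, and it is why the point is minor. It does not make the omission reasoned: once a treatment-effect model is specified, its covariates should follow the design or the departure should be explained.

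The magnitude can also be challenged. It depends on assumed effects and borrows 30%, 50% and 0.10 from two one-sample designs. In row (a) the inert case still shows +0.8, so part of that gain is discreteness rather than prognostic adjustment. In row (b) the weak-case gain of 0.6 is within two standard errors of zero. These are fair limits on the figures. Row (c) does cover the covariates the plan names, and it points the same way, but with few trials.

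Last, the model becomes heavier. With 0.30×50 + 0.50×50 = 40 responders, treatment, load and seven site terms make 9 parameters (40/9 = 4.4 responders each); three more make 12 (3.3 each). That is a real cost and a reason to settle how site is handled.

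Section 12.3 does plan marker analyses between the arms, but these concern markers. They are not a treatment comparison of response.

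**Conclusion.** The concern holds, as a minor one. Both exact logistic models in Section 13.2, and by extension the iRECIST version, omit the two factors used to stratify randomization, and the documents give no reason. The per-arm response rates, their 90% intervals and the sample size are unaffected. Under the stated assumptions the omission costs about 0 to 4 points of power and shrinks the log odds ratio by about 2 to 12% when the factors are weakly to strongly prognostic. If they do not predict response, the loss is essentially nil. Confidence is high that the factors are omitted without explanation. The size is only indicative, because the documents give no effect of ECOG status or prior treatment on response.

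**What to change.** In both places in Section 13.2, add ECOG (0, 1) and number of prior treatments (0, 1-2, 3 or more), as randomized, to the adjustment set. Enter them as main effects beside mutational load, or use them as the conditioning strata.

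- Do not cross them with site: 6 strata × 8 sites = 48 cells, about 2 patients each (100/48). Do not cross them with load either; crossing load with the six strata changes power by −2.4, −2.4, −1.1 and +1.4 points from inert to strong.
- Pre-specify merging 0 with 1-2 prior treatments if the 0 level is sparse. Section 4.1.2 restricts treatment-naive entry; if 10% are naive, that is 10 patients, about 5 per ECOG level. Four strata perform like six: 58.5, 59.1, 60.4 and 62.0% against 58.6, 58.9, 60.5 and 61.9%.
- Keep mutational load. Section 2.3 supports it: "tumor mutational burden associates with sensitivity to checkpoint blockade with PD-1 blockade".
- State whether site stays in this model or goes into a separate one.

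Alternatively, add one sentence explaining why the stratification factors are left out.

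The change is to wording and needs no new data. Because the text sits in the protocol's statistical section, it may have to go through an amendment. The statistical price is three more terms in a small exact model (two if the prior-treatment levels are merged), with no real gain if the factors turn out not to predict response.

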## TREATMENT SCHEMA

This is an international multi-center, open-label, randomized phase II non-comparative trial of nivolumab alone or in combination with ipilimumab for the treatment of patients with advanced hypermutated solid tumors detected by a blood based assay. The biomarker selection of eligible patients will initially be based on detection of either POLE or POLD1 mutations by cfDNA or tumor testing.

[figure not shown]
Tumor testing may be conducted in a clinical laboratory as part of standard assessment.

For patients that do not have tumor testing, eligible and consenting patients will undergo screening for POL mutations by testing of cfDNA.

Eligible and consenting patients with POLE or POLD1 mutations will be randomized 1:1 into two arms.

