**4.2 Additional Criteria To Be Met Prior To Study Enrollment**

All patients must fulfil all of the following criteria to be eligible for randomization to the study.

4.2.1 Patients must have solid tumors that demonstrate POLE or POLD1 mutations identified at study entry via plasma cfDNA testing or tumor tissue testing for POLE and POLD1 mutations. A CLIA-certified testing of tumor tissue demonstrating POLE or POLD1 mutation can qualify for eligibility and randomization, however plasma will be submitted for central cfDNA testing. In the event of discordance between tissue and central laboratory testing, the patient will continue in study but will not be included in the primary analysis. These patients will however be included in the secondary analysis.

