## 5.1 Follow-up for Patients

The follow-up requirements for ineligible randomized patients who have received no protocol therapy include submission of the Baseline Report and an End of Treatment Report. Data submission for ineligible participants who have received at least one dose of protocol therapy should be according to the protocol to allow for treatment and adverse event assessment. For patients without detectable POLE or POLD1 mutations on cfDNA screening, no follow-up is required.

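### The tumor–blood objective rests on a per-arm Fisher test in patients selected for a positive result; the tissue result and table are unspecified, and the test does not measure agreement

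*Combined protocol and SAP*

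**What the plan says.** Section 1.2 lists as a secondary objective the correlation between POLE/POLD1 mutations in tumor and in blood. The only analysis for it is in section 13.2: "Correlation between detectable mutations in tumor and detectable mutations in blood will be assessed by Fischer's exact test in each arm". No table layout, effect measure, interval or rule for missing tissue is given, and section 13.2 defines a detectable mutation by plasma cfDNA only.

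The population is selected on the same two variables. Section 4.2.1: "Patients must have solid tumors that demonstrate POLE or POLD1 mutations identified at study entry via plasma cfDNA testing or tumor tissue testing". Section 12.1.1 makes patients without a mutation ineligible. For screen failures, section 5.1 states: "For patients without detectable POLE or POLD1 mutations on cfDNA screening, no follow-up is required".

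There are two entry routes.
- **Plasma.** The Treatment Schema states: "For patients that do not have tumor testing, eligible and consenting patients will undergo screening for POL mutations by testing of cfDNA". These patients ordinarily have no tumor result at entry.
- **Tissue.** Section 12.1.1 accepts any CLIA-certified tissue assay, and "patients randomized on the basis of archival tumor testing will have cfDNA testing of peripheral whole blood performed retrospectively".

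A second tumor result may come later. Under section 12.1.2 tissue is mandatory and "these samples are expected to be submitted upon randomization for all patients", and POLE/POLD1 status heads the list of assays planned on it. Tissue-entered patients with no remaining material are nevertheless not excluded (sections 4.2.4 and 12.1.2).

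**The concern.** Fisher's exact test asks whether two binary results are associated, given the margins of a 2×2 table. That table needs patients negative on both results, and eligibility removes them, wholly or partly. Two tissue results are possible and section 13.2 names neither, so the table is not fixed in advance and could be chosen after the data are seen.

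Even with a fixed table, a p-value for association does not answer what a reader of a blood-selected trial will ask: how often plasma finds a mutation reported in tumor, and how often tumor carries one found in plasma. That matters here because patients positive in tissue but not in plasma are left out of the primary analysis. Splitting by arm has no evident purpose, since the eligibility plasma is drawn before randomization, and it halves the sample.

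At stake is the interpretability of one secondary objective.

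**Working it through.** The plan states no sample size, power or alpha for this analysis, so there is no figure to reproduce. All table counts below are assumptions, per arm, written as both positive / tissue only / plasma only / both negative = a/b/c/d. From section 13.3: 50 evaluable patients per arm, plus up to 20% more to replace patients negative on central cfDNA. That is at most 0.20 × 50 = 10 tissue-only patients per arm if split evenly.

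**Reading (a): entry tissue results only.** Nearly everyone with a tissue result is tissue-positive, so the table has essentially one row. Example 30/10/0/0: odds ratio undefined, p = 1.0.

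**Reading (b): qualifying report for tissue-entered patients, later assay for plasma-entered patients, scored as any POLE/POLD1 mutation.** Everyone is positive on at least one result, so d = 0.
- Odds ratio = (a × d)/(b × c) = 0, or undefined if b or c is 0.
- With the margins fixed, the smallest possible both-positive count is (a + b) + (a + c) − (a + b + c) = a, which is the observed count. The one-sided p for positive association, P(X ≥ a), is therefore always 1. Enumeration agrees: 1.0 in all 1,326 tables with n = 50 and all 1,891 with n = 60.
- A small two-sided p can then only be a negative association, and selection produces it.

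Two-sided p for 50 plasma-positive plus 10 tissue-only patients; the odds ratio is 0 in every row:

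| Table | p |
|---|---|
| 48/10/2/0 | 1.0 |
| 42/10/8/0 | 0.33 |
| 40/10/10/0 | 0.19 |
| 37/10/13/0 | 0.099 |
| 34/10/16/0 | 0.0495 |
| 30/10/20/0 | 0.023 |

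So p < 0.10 needs at least 13 of 50 plasma-positive patients without a tissue mutation, and p < 0.05 at least 16 of 50. With only 5 tissue-only patients the thresholds rise to 22 of 50 (p = 0.076) and 28 of 50 (p = 0.023).

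**Reading (c): research assay for everyone.** A tissue-entered patient can now be negative on both, so d need not be 0. The same 50 patients:
- Qualifying results, 44/4/2/0: agreement 44/50 = 88%, odds ratio 0, p = 1.0.
- Two of the four tissue-only results not reproduced, 44/2/2/2: agreement 46/50 = 92%, odds ratio (44 × 2)/(2 × 2) = 22, p = 0.028.

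Agreement moves by 4 percentage points, while the test moves from no evidence to a strong positive association.

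**Association is not agreement, even without selection.** 25/5/5/15 agrees in 40/50 = 80% and 5/25/15/5 in 10/50 = 20%. Both give two-sided p = 0.00007.

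**The case against.** The best defence is that reading (c) is the natural one. Section 12.1.1 requires plasma-entered patients to have tissue for analysis, and section 12.1.2 expects it from all randomized patients and puts POLE/POLD1 first among the assays. Comparing that assay with central cfDNA avoids the forced zero. So does scoring each gene separately, because a patient with POLD1 mutations in both samples is double-negative for POLE; assumed POLE counts of 30/3/0/17 give a Fisher p of about 1e-10. Reading (a) is not strictly one row either, since a patient with an earlier negative tissue test could qualify by plasma. Finally, the objective says correlation, for which a test of association is a recognizable choice, and false significance under (b) needs heavy discordance in both directions.

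Much of this stands. The zero cell is conditional on the reading, and under (b) the usual result is an uninformative p-value rather than a misleading one. It does not rescue the plan. Section 13.2 names none of these readings; the research result may be missing for tissue-entered patients; and selection still shapes the table under (c). If correlation is meant literally, a p-value gives no strength of correlation. Naming the tissue result and the table would be a smaller repair, but would still leave the rate of agreement unreported.

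**Conclusion.** The concern holds, at minor severity. Three statements need no assumed counts: the tissue result and the table are unspecified; where the double-negative cell is empty by eligibility, positive association cannot be shown; and under every reading Fisher's test leaves agreement unmeasured. The size of the effect does rest on assumed counts, on tissue-only patients splitting evenly between arms and, for the zero cell, on reading (b). The primary response-rate analysis is unaffected.

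**What to change.** In section 13.2, replace the Fisher test with two proportions pooled over both arms, each with the exact 90% interval that section already uses for response rates, and reported separately by entry route:

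1. Among tissue-entered patients, the proportion positive on central plasma cfDNA. This is positive percent agreement with the qualifying tissue report. Note that different tissue assays are accepted and that archival tissue may predate the plasma sample.
2. Among plasma-entered patients with a tissue result, the proportion tissue-positive on the research assay. Label it a positive predictive proportion and do not combine it with (1).

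State that positive means any POLE/POLD1 mutation, that the tissue result is the qualifying report in (1) and the research assay in (2), and that negative agreement cannot be estimated in this selected population. Where the research assay is also run on tissue-entered patients, list unreproduced qualifying results descriptively. By-arm proportions may be added.

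Assumed illustration: 40 tissue-entered and 80 plasma-entered patients, equivalent to 42/10/8/0 in each arm. Fisher gives odds ratio 0 and p = 0.33 per arm. The replacement gives:

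| Proportion | Pooled (90% CI) | Per arm (90% CI) |
|---|---|---|
| (1) | 20/40 = 50% (36.1–63.9%) | 10/20 = 50% (30.2–69.8%) |
| (2) | 64/80 = 80% (71.2–87.0%) | 32/40 = 80% (66.8–89.6%) |

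The cost is one paragraph and no new samples: (1) uses the retrospective cfDNA testing already mandated in section 12.1.1, and (2) uses tissue already required of plasma-entered patients. The drawbacks are that the objective no longer has a single p-value and that (1) mixes tissue assays.
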